## 7.5 Efficacy Analysis

Tumor response will be evaluated using RECIST 1.1 criteria ([Eisenhauer, 2009](#)). Tumor burden will be characterized prior to enrollment, and response assessments will be at approximately every 9 weeks starting from C1D1. A confirmed BOR of CR or PR requires the confirmation occurring at least 4 weeks after initial documentation. A BOR of SD requires a minimum of 63 days on study from C1D1 to the date of the first imaging assessment., Disease assessment at both scheduled and unscheduled visits will be used for efficacy endpoints. Disease assessments after new systemic anti-cancer therapy, surgical procedures or radiotherapy on target lesions will be excluded. Treatment beyond progression is allowed for qualified subjects. However, tumor assessment beyond progression will not be considered for response endpoints.

For efficacy endpoints including ORR, CBR, BOR summary will be based on the response-evaluable population. DOR and TTR will be summarized among confirmed responders. PFS, OS will be analyzed in the safety population. In addition, swimmer plot of tumor response and waterfall plot of best tumor size change will be generated based on safety population. Separate summary table and figures for efficacy analyses will be generated for HNSCC and CRC patients.

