**Table 1: Schedule of Visits and Assessments – Phase 1b (CRC and HNSCC; NKTR-255 Dose Escalation) (Contd)**

Event a	Screening Period	Treatment Period																		Post-treatment Period									
		Run-in (1 week) Day			Cycle 1 (21-day cycle) Day						Cycle 2 (21-day cycle) Day						Cycle 3 (21-day cycle) Day			Cycle 4+ (21-day cycles) Day									
		≤ 28d prior to Day 1 of Run-in Period			-7	-6	-4	1	2	3	4	5	8	10	15	1	2	3	4	8	10	15	1	4	8	15	EOT b	60-day Follow-up c	Survival Follow-up c
Windows (days)		+1			+1										+1							+1			+1		+7	±14	Every 3 months ±14 days
Study Drug Administration																													
NKTR-255 administration u						X									X							X			X				
Cetuximab administration v			X			X				X	X	X				X		X	X	X	X	X	X	X					
Concomitant medications review	Continuous from time of ICF until 60 days after last study treatment dose																												
Efficacy Assessments																													
Tumor measurements and RECIST 1.1 and irRECIST response assessments w	Tumor assessments at Screening and every 9 weeks from C1D1 + 7 days until patients meet one of the criteria for discontinuation of treatment in Section 5.2.3.1.																												
Subsequent therapy/survival/secondary malignancy information																							X	X	X				

AE = adverse event;  $\beta$ -HCG = beta subunit of human chorionic gonadotropin; CK = creatine kinase; CnDn = Cycle n Day n; CRC = colorectal cancer; d = day; ECG = electrocardiogram; EBV = Epstein-Barr virus; ECOG = Eastern Cooperative Oncology Group; EOI = end of infusion; EOT = end of treatment; HBV = hepatitis B virus; HCV = hepatitis C virus; HIV = human immunodeficiency virus; HNSCC = head and neck squamous cell carcinoma; HPV = human papillomavirus; ICF = informed consent form; irRECIST = immune-related RECIST 1.1; IV = intravenous(ly); LVEF = left ventricular ejection fraction; MRI = magnetic resonance imaging; MUGA = multigated acquisition; PaO2 = oxygen saturation; CCI [REDACTED] PK = pharmacokinetic(s); PT = prothrombin time; PTT = partial thromboplastin time; q21d = every 21 days; q3 = every 3; RECIST = Response Evaluation Criteria In Solid Tumors; T3 = triiodothyronine; T4 = thyroxine; TSH = thyroid-stimulating hormone; WCBP = women of childbearing potential

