## **8.0 ASSESSMENT OF EFFICACY**

### **8.1 Treatment Response Assessment**

Tumor response will be evaluated using RECIST 1.1 criteria ([Eisenhauer, 2009; Appendix 2](#)).

Tumor burden will be characterized prior to enrollment, and response assessments will be performed approximately every 9 weeks starting from C1D1.

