### **8.2 Tumor Imaging (Computed Tomography or Magnetic Resonance Imaging)**

Computed tomography (CT) with contrast or magnetic resonance imaging (MRI) (for patients who cannot tolerate CT contrast) will be obtained to document metastatic disease, identify target lesions as described in RECIST 1.1, and to assess response and disease progression. Imaging by CT scan with contrast or MRI will be performed at Screening, and approximately every 9 weeks during the treatment period regardless of cycle number or dose interruption.

Scans taken as part of standard medical practice up to 42 days prior to first dose of study treatment can be used for Screening. During the treatment, scans may be performed at timepoints other than every 9 weeks as clinically indicated to assess tumor progression. A standard-of-care brain MRI occurring prior to the 28-day screening window may be acceptable based on consultation with the Medical Monitor.

The text 'CCI' is displayed in a large, bold, red font, centered on a solid black rectangular background.

At Screening, a brain MRI is only required for patients with a history of brain metastases and should be followed as clinically indicated. Other scans may be included as clinically indicated.

For patients who stop study treatment in the absence of disease progression (eg, due to unexpected toxicity), scans should continue to be collected approximately every 9 weeks until disease progression or initiation of systemic anti-tumor therapy other than the study treatment (whichever is earlier) or unless patient withdraws consent.

The same imaging procedure and specifications (eg, contrast agent, scanner, slice thickness, etc.) used to define measurable target and non-target lesions must be used throughout the study for each patient.

Computed tomography scans may not be performed at sites or in countries where additional radiology approval is required, unless that approval is sought and granted.

The text 'CCI' is displayed in a red font, centered on a solid black rectangular background.

CCI

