## 6.0 STATISTICAL CONSIDERATIONS

### 6.1 General Considerations

The statistical analyses will be reported using summary tables, data listings and graphics as appropriate.

Unless otherwise specified, data collected during the dose escalation phase will be presented by dose level groups and overall. Continuous variables will be summarized with means, standard deviations, medians, minimums, and maximums. The means will be presented to one decimal place beyond which the data were captured. The standard deviation will be presented to two decimal places beyond which the data were captured. The minimum and maximum will be presented to the precision with which the data were captured.

Categorical variables will be summarized by counts and by percentage of subjects in corresponding categories. A row or column denoted 'Missing' will be included in count tabulations where necessary to account for dropouts and missing values. Percentages will be rounded to 1 decimal place and the percent will be suppressed when the count is zero. The denominator will be the number of subjects in the cohort of interest unless otherwise noted.

Unless specified otherwise, all 95% confidence interval for proportions will be two-sided and be based on the exact (Clopper-Pearson) method and confidence interval for the quartiles of time to event variables will be based on the Brookmeyer and Crowley method using log-log transformation (1982).

For analyses by visit, only data of scheduled visits will be reported, and nominal visits will be used. For analyses up to a certain time point, data of both scheduled visits and unscheduled visits up to that time point will be considered. For analyses of worst post-baseline value, both scheduled and unscheduled measurements will be included.

For BOR and PFS, both scheduled and unscheduled assessments will be included. The actual investigator response assessment dates will be used.

[figure not shown]

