**Treatment-emergent adverse events (TEAE):**

- Any AE that occurs after study treatment initiation.
- An AE that was present at the time of study treatment initiation but worsened after study treatment initiation.
- An AE that was present and resolved prior to treatment and reappeared after treatment initiation.
- Any treatment-related AE will always be considered treatment-emergent.

**NKTR-255 Treatment-emergent adverse events (TEAE) period:** Start of NKTR-255 through 30 days post last dose NKTR-255, or until a new antineoplastic regimen has been initiated, whichever comes first.

**Extended treatment-emergent adverse events (TEAE) period:** Start of any study drug through 60 days post last dose of study drug, or until a new antineoplastic regimen has been initiated, whichever comes first.

**Prior medications:** Prior medications are defined as medications with start date prior to C1D1.

**Concomitant medications:** Concomitant medications are defined as medications with stop date after C1D1, or medications with start date on or after C1D1 and up to 30 days after the last dose of NKTR-255. Medications with a start date after the initiation of any subsequent anticancer treatment will not be considered concomitant medications.

Medications with start date prior to C1D1 and end date after C1D1 will be classified as both prior and concomitant medications.

**Best overall response (BOR):** The BOR is defined as the confirmed best response designation over post-baseline response assessments. Disease assessments beyond progression or after start of subsequent therapy will not be considered for BOR.

**Overall response rate (ORR):** The ORR is defined as the proportion of subjects who have achieved PR or better as their BOR.

**Complete response rate (CRR):** The CRR is defined as the proportion of subjects who have achieved CR as their BOR.

**Responders:** Responders are defined as subjects with a confirmed BOR of PR or better. Ongoing responders are defined as responders who have not progressed, not died, not been off study and not started a subsequent therapy.

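### The SAP tests the 63-day minimum for stable disease on the first scan, so a patient whose first scan is early and shows no progression cannot be classed as SD, whatever later scans show

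*SAP*

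**What the plan says.** SAP 7.5 sets the rule for stable disease: "A BOR of SD requires a minimum of 63 days on study from C1D1 to the date of the first imaging assessment". The screening scan precedes C1D1, so the first imaging assessment must mean the first scan after C1D1.

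Other provisions determine which scan that can be:

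- Protocol Table 1 schedules imaging as follows: "Tumor assessments at Screening and every 9 weeks from C1D1 + 7 days". The window is positive only. Protocol 8.1 and SAP 7.5 describe the interval more loosely, as approximate.
- Protocol 8.2 permits additional imaging: "scans may be performed at timepoints other than every 9 weeks as clinically indicated to assess tumor progression".
- SAP 6.1 brings those scans into the endpoint: "For BOR and PFS, both scheduled and unscheduled assessments will be included". SAP 7.5 says the same in the sentence after the SD rule: "Disease assessment at both scheduled and unscheduled visits will be used for efficacy endpoints".
- SAP 6.6.1 defines the endpoint over the whole series: "The BOR is defined as the confirmed best response designation over post-baseline response assessments".

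SAP 7.5.1 counts CR, PR and SD in CBR. SAP 6.3 makes a patient response-evaluable with a single post-baseline tumor assessment, given measurable disease at baseline and a dose of NKTR-255.

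**The concern.** The date of a first scan is fixed once the scan is done. If it falls before day 63, no later scan can satisfy a rule that ends at that date. Neither document says that a later SD scan may satisfy the minimum, or that early unscheduled scans are ignored for this test.

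The outcome is perverse. Take two patients who are both stable at days 63 and 126, one of whom was also scanned and found stable at day 40. The second has more evidence of stability, yet is the one refused SD. Unscheduled scans are done because progression is suspected, so the loss falls on patients whose symptoms prompted a scan that showed none.

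The affected patient leaves the CBR numerator but stays in the denominator, so the error in CBR runs in one direction. The SAP also does not say which BOR category that patient receives, which leaves the choice to programming, possibly after the data are known.

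**Working it through.** Days below are counted from C1D1.

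**Step 1. Reproduce the threshold.** 9 weeks × 7 = 63 days, the SAP's figure. With the +7-day window in Protocol Table 1, a scheduled first scan falls on days 63 to 70 and passes. Under the SAP 6.5 duration formula (later date − earlier date + 1) the same scan counts as 64 to 71 days and also passes. On-schedule patients are unaffected.

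**Step 2. Apply the rule to example scan sequences.** The literal rule asks whether the first scan is at 63 days or more. The repaired rule asks whether any scan showing SD or better, before PD, is at 63 days or more.

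| Scan sequence | Literal rule | Repaired rule |
|---|---|---|
| SD day 63, SD day 126, PD day 189 | SD | SD |
| SD day 40 (unscheduled), SD day 63, SD day 126, PD day 189 | not SD | SD |
| SD day 40 (unscheduled), PD day 63 | not SD | not SD |

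The results are the same with or without the + 1 of SAP 6.5. Only the second row changes: an early first scan followed by qualifying stability. A patient with an unconfirmed response, who would otherwise default to SD, is caught in the same way.

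**Step 3. Who is not affected.** Patients with a confirmed CR or PR do not need the SD category. Patients who progress before day 63 are not SD under either rule. Unscheduled scans after the first scheduled scan do not change the date of the first one.

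**Step 4. Effect on CBR.** CBR = (CR + PR + SD) / n. Each affected patient is removed from the numerator only, so CBR falls by 1/n:

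- n = 30 (the planned Phase 1b size, assuming all are response-evaluable): 1/30 = 3.3 points.
- n = 15 (assuming an even split between HNSCC and CRC, which SAP 7.5 reports separately): 1/15 = 6.7 points.

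**Step 5. Illustration.** The documents give neither expected response rates nor the number of early scans. Assume 3 confirmed responders and 12 SD patients among 30, and 2 responders and 6 SD patients among 15. Intervals are exact 95% (Clopper-Pearson), as in SAP 6.1.

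| SD patients with an early first scan | CBR, n = 30 | CBR, n = 15 |
|---|---|---|
| 0 | 15/30 = 50.0% (31.3–68.7) | 8/15 = 53.3% (26.6–78.7) |
| 1 | 14/30 = 46.7% (28.3–65.7) | 7/15 = 46.7% (21.3–73.4) |
| 2 | 13/30 = 43.3% (25.5–62.6) | 6/15 = 40.0% (16.3–67.7) |
| 4 | 11/30 = 36.7% (19.9–56.1) | 4/15 = 26.7% (7.8–55.1) |

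**The case against.** The best defense is intent. Sixty-three days is exactly the first scheduled visit, so the authors probably meant that SD must be seen at or after that visit. A programmer guided by the SAP 6.6.1 definition of BOR might code it that way. That is plausible, but the text does not say so, and the very next sentence brings unscheduled assessments in. The likely intent is a reason to write it down.

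The second defense is that little depends on it. CBR is descriptive, it is not among the visible primary or secondary endpoints for Phase 1b, and no visible decision rule uses it. The SD minimum does not enter ORR, DOR, PFS or OS. The error understates disease control, and the swimmer plot would still show a long stable course. The intervals in the illustration overlap heavily. All of this stands, and it limits the weight of the point.

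A reader might also infer that a scheduled scan done a few days early is a routine route to the same loss, since Protocol 8.1 and SAP 7.5 call the interval approximate. The documents give this little support. Table 1 allows only +7 days, and a scan before day 63 without a clinical reason is out of window and recorded as a protocol deviation. If the SAP 6.5 formula applies, a scan one day early counts as 62 + 1 = 63 days and passes.

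**Conclusion.** The rule is wrong as written, within a narrow scope. It misclassifies a patient only when the first scan after C1D1 is before day 63, that scan does not show progression, and the BOR would otherwise be SD. In that case the literal text contradicts the SAP's own definition of BOR.

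It would be tempting to conclude that any early unscheduled scan lowers CBR, or that the trial's efficacy results as a whole are biased downward. The documents do not support either: confirmed responders and patients who progress before day 63 are untouched, and ORR, PFS and OS do not use the rule.

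The size is 1/n per affected patient: 3.3 points at 30 and 6.7 points at 15. The 30 assumes that every planned patient is response-evaluable, and the 15 assumes an even split by tumor type. The number of affected patients cannot be taken from the documents and may be zero.

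**What to change.** Replace the SD sentence in SAP 7.5 with:

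> A BOR of SD requires at least one assessment of SD or better dated 63 days or more after C1D1, before disease progression and before any new anti-cancer therapy, regardless of earlier non-progression scans. Patients with neither PD nor a confirmed CR or PR who do not meet this are classified as not evaluable.

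The limit to assessments before progression is needed because Protocol 5.2.5 permits treatment beyond progression. Without it, PD at day 40 followed by an SD reading at day 70 would qualify, contrary to SAP 6.6.1 and 7.5. The other exclusions in SAP 7.5 continue to apply. State also that patients classed as not evaluable stay in the CBR denominator, in line with the response-evaluable definition, and whether the + 1 of SAP 6.5 applies to the 63 days.

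The cost is a short edit to the SAP and the matching line in the BOR derivation. It needs no new data and no change to the scan schedule.

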### 6.3 Analysis Populations

**Enrolled Population:** All patients who receive at least 1 dose (or partial dose) of cetuximab or NKTR-255.

**Safety Population:** All patients who receive at least 1 dose (or partial dose) of NKTR-255.

**Cetuximab-only Population:** All patients who receive at least 1 dose (or partial dose) of cetuximab but without any dose of NKTR-255.

**DLT Population:** All patients who receive at least 1 dose of the combination treatment of NKTR-255 and cetuximab and who complete the DLT observation period or discontinue from

the study treatment due to a DLT will be included, where DLT window is 21 days since the first dose of NKTR-255.

**Response-evaluable Population:** The Response-evaluable Population is defined as patients who have measurable disease (per RECIST 1.1) at baseline, receive at least 1 dose (or partial dose) of NKTR-255, and have at least 1 post-baseline assessment of tumor response.

**Pharmacokinetic Population:** All patients in the Safety Population who receive at least 1 dose of treatment and have at least one evaluable PK concentration.

CCI

CCI

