## 6.5 Conversion between Day, Month and Year

Conversions between different time unit will be based on days. For conversion to month and year, the following formula are used: month=days/30.4375, year=days/365.25.

Days of duration and time to events are calculated with the following formula:

(later assessment or study treatment [or follow-up] end date) – (earlier assessment or study treatment start date) +1.

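### Response rates leave out treated patients who were never assessed, and the stable-disease minimum is tied to the first scan, so an early scan can void later stable disease

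*SAP*

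**What the plan says.** On the denominator, SAP 7.5 states: "For efficacy endpoints including ORR, CBR, BOR summary will be based on the response-evaluable population". Under SAP 6.3 that set needs measurable disease at baseline, at least one full or partial dose of NKTR-255, and patients must "have at least 1 post-baseline assessment of tumor response". Protocol 9.5 and 9.6.3 already carried the post-baseline requirement and used the same population for response, so the restriction is pre-specified. In the Safety Population, SAP 7.5 plans PFS and OS, and adds that a "swimmer plot of tumor response and waterfall plot of best tumor size change will be generated based on safety population". SAP 7.1 reports how many patients fall in each population.

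On stable disease, SAP 7.5 states: "A BOR of SD requires a minimum of 63 days on study from C1D1 to the date of the first imaging assessment". The same section says: "Disease assessment at both scheduled and unscheduled visits will be used for efficacy endpoints". SAP 6.1 agrees: "For BOR and PFS, both scheduled and unscheduled assessments will be included". Protocol 8.2 permits scans off the 9-week schedule when clinically indicated. SAP 6.6.1 defines best overall response without reference to the first scan: "The BOR is defined as the confirmed best response designation over post-baseline response assessments".

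**The concern.** This is a salvage regimen, and the first scheduled scan comes about 9 weeks after C1D1. A treated patient who dies, deteriorates or withdraws before any scan is not counted as a failure; the patient is not counted at all. Results are shown by dose level (SAP 6.1) and by tumor type (SAP 7.5), so denominators are small and one such patient moves a rate visibly. The reader gets no all-treated ORR, CBR or confidence interval.

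The SD sentence raises a different problem. If the 63 days are measured to the first scan of any kind, a patient scanned early for a clinical reason fails the minimum for good, however long the disease then stays stable. That does not fit a BOR taken over all post-baseline assessments. The SAP also does not name the BOR category for a patient who misses the minimum, although SAP 7.5.1 tabulates BOR by category.

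**Working it through.** The plan states no ORR, CBR or never-assessed rate for Phase 1b, so there is no figure to reproduce. The counts below are illustrations.

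**Inputs.** About 30 patients in Phase 1b, at least 3 per dose level and at least 6 to define the RP2D (SAP 5.0). Scans every 9 weeks from C1D1 with a +7-day window (Protocol 1.2, Table 1), so a first scheduled scan falls 63 to 70 days after C1D1. Exact Clopper-Pearson intervals (SAP 6.1). SD minimum of 63 days (SAP 7.5).

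**Direction of ORR.** Let n be the treated patients with measurable disease, m those never assessed, x the responders, and d = m/n. A responder needs a post-baseline assessment, so x is the same in both sets:

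response-evaluable ORR = x/(n − m) = (x/n) × 1/(1 − d) ≥ x/n

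Equality holds only if m = 0 or x = 0. The statement is limited to patients with measurable disease. A responder without it would also be excluded and could lower ORR (6/30 = 20.0% becomes 5/29 = 17.2%), but inclusion criterion 8 (Protocol 4.1.1) makes that unlikely.

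**Size for ORR**, assuming n = 30 and x = 3:

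| Never assessed | Multiplier | ORR | Exact 95% CI |
|---|---|---|---|
| 0 (0%) | 1.00 | 3/30 = 10.0% | 2.1 to 26.5 |
| 3 (10%) | 1.11 | 3/27 = 11.1% | 2.4 to 29.2 |
| 6 (20%) | 1.25 | 3/24 = 12.5% | 2.7 to 32.4 |
| 9 (30%) | 1.43 | 3/21 = 14.3% | 3.0 to 36.3 |

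At the plan's own group sizes, one unassessed patient moves 1/6 = 16.7% (0.4 to 64.1) to 1/5 = 20.0% (0.5 to 71.6), or 1/3 = 33.3% (0.8 to 90.6) to 1/2 = 50.0% (1.3 to 98.7).

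**SD rule, read literally.** SAP 6.5 has a general duration formula that ends "earlier assessment or study treatment start date) +1". SAP 7.5 does not say whether its 63 days follow that formula or are a plain date difference. Both are shown:

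| First scan, days after C1D1 | With +1 | Result |
|---|---|---|
| 42 | 43 | fails on both counts |
| 61 | 62 | fails on both counts |
| 62 | 63 | passes only with +1 |
| 63 | 64 | passes on both counts |
| 70 | 71 | passes on both counts |

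A patient with SD on an unscheduled scan at 42 days and SD again at weeks 9, 18 and 27, with no confirmed response, cannot have a BOR of SD. First scans taken within the scheduled window all pass.

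**Effect on CBR.** Each voided SD patient lowers CBR by 100/n points: 4.2 for n = 24, 16.7 for n = 6, 33.3 for n = 3.

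**Both effects together.** Assume 12 of 30 treated patients have CR, PR or SD (40.0%), 6 are never assessed, and k SD patients are voided. The plan then shows (12 − k)/24: 50.0%, 45.8%, 41.7% or 37.5% for k = 0, 1, 2 or 3. Break-even is (12 − k)/[30(1 − d)] = 12/30, so k = 12d: 1.2, 2.4 or 3.6 for d = 10, 20 or 30%. CBR may therefore be overstated or understated.

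**The case against.** The strongest case is that little depends on these rates. The primary Phase 1b endpoints are DLTs and TEAEs (SAP 4.1), the readable secondary ORR endpoint names other tumor types (SAP 4.2), no Phase 2 patients were enrolled, and the summaries are descriptive. The response-evaluable set was pre-specified. PFS and OS use the Safety Population, so a death before any scan counts as an event in both. Scanning should continue after treatment stops (Protocol 5.2.3.1 and 8.2), and an unscheduled scan keeps a patient in the set. A crude all-treated rate can be worked out from the disposition counts. All of this stands and limits the impact. It is a partial offset: a living patient who is never scanned is censored for PFS at the first cetuximab dose (SAP Table 3), and neither plot gives a rate or an interval. Some text is redacted, so the absence of an all-treated rate can be stated only for what is readable.

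On SD, 63 days is exactly 9 weeks, so the sentence may mean the first scheduled scan. That is a reasonable guess at intent, but the text does not say it, and a programmer could code either reading. A scheduled scan at 61 days would be outside the +7-day window and a protocol deviation, yet Protocol 8.2 also calls the interval approximate. The SAP 6.5 formula probably settles the day count; only a scan at 62 days depends on it.

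**Conclusion.** Both points hold. Among treated patients with measurable disease, the planned ORR can only equal or exceed the all-treated ORR, by the factor 1/(1 − d), and no all-treated ORR, CBR or interval is planned in the readable text. The direction is arithmetic. The size depends on d and on response counts, neither of which the documents give. Read literally, the SD rule removes durable SD from BOR and CBR because of one early scan, at 1/n per patient; first scans within the scheduled window are unaffected. The net bias in CBR is undetermined. Because Phase 1b efficacy is descriptive and drives no Go/No-Go rule, this should be corrected in the SAP but does not threaten the trial's main conclusions.

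**What to change.** 1. Keep the response-evaluable summary. Beside it, report ORR, CBR and BOR with exact 95% CIs in the Safety Population with measurable disease at baseline, by tumor type and overall. Show patients with no post-baseline assessment as not evaluable and count them as non-responders.
2. Reword the SD minimum so that any assessment of SD or better at least 63 days from C1D1, before progression or new anti-cancer therapy, satisfies it.
3. State the day count. Scan date − C1D1 + 1 ≥ 63 follows SAP 6.5.
4. Name the BOR category for patients who miss the minimum.

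The cost is some SAP wording and one extra column in existing tables; no new data are needed. ORR in the added column can only be equal or lower. With the day count unchanged, or with the +1 count, the new SD rule can only raise CBR or leave it the same. If the current rule is read with +1 and the new one used a plain difference, SD seen only at 62 days would be lost.
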